#### **Adverse Events Attribution**

Attribution is the determination of whether an adverse event is related to a medical treatment or procedure.

Definite - the adverse event is clearly related to the investigational agent(s).

Probable - the adverse event is likely related to the investigational agent(s).

Possible - the adverse event may be related to the investigational agent(s).

Unlikely - The adverse event is doubtfully related to the investigational agent(s).

Unrelated - The adverse event is clearly NOT related to the investigational agent(s).

#### **Adverse Events Severity**

The severity of the adverse events (AEs) will be graded according to the U.S. Department of Health and Human Services, National Institutes of Health, National Cancer Institute, Common Terminology Criteria for Adverse Events (CTCAE), Version 5.0.

Events not included in the NCI CTCAE will be scored as follows:

- Grade 1: Mild: discomfort present with no disruption of daily activity, no treatment required beyond prophylaxis.

- Grade 2: Moderate: discomfort present with some disruption of daily activity, require treatment.
- Grade 3: Severe: discomfort that interrupts normal daily activity, not responding to first line treatment.
- Grade 4: Life Threatening: discomfort that represents immediate risk of death

The investigator (or physician designee) is responsible for verifying and providing source documentation for all adverse events, assigning the attribution and assessing the severity of the AE, the causal relationship between any events and the clinical study procedure, activities or device. Additionally, the Investigator is responsible for providing appropriate treatment for the event and for adequately following the event until resolution for all adverse events for subjects enrolled.

The Principal Investigator will sign and date the AE log per each subject at the completion of each course. Following signature, the AE log will be used as source documentation for the adverse events for attribution.

All participants will be registered in the Clinical Oncology Research System (CORE)

**The Leukemia-specific Adverse Event Recording and Reporting Guidelines** will be followed for the recording and reporting of adverse and serious adverse events.

Baseline events will be recorded in the medical history section of the case report form and will include the terminology event name, grade, and start date of the event. The medical history section of the case report form will serve as the source document for baseline events once signed and dated by the principal investigator.

**Baseline events** are any medical condition, symptom, or clinically significant lab abnormality present before the informed consent is signed

**Hematologic laboratory abnormalities** will not be recorded as baseline events for subjects with acute leukemia, myelodysplastic syndrome, chronic lymphocytic leukemia, or chronic myeloid leukemia in blast phase.

If exact start date is unknown, month and year or year may be used as the start date of the baseline event.

All grades of the adverse event will be captured per course or protocol defined visit date. For adverse events that increase or decrease in grade, the stop date should reflect the date that the event changed grade and a new start date should be added for the new grade.

**Hematologic adverse events** will not be recorded or reported for studies in subjects with acute leukemia, except for:

- Prolonged myelosuppression as defined by the NCI-CTCAE criteria specific for leukemia, e.g. marrow hypocellularity on day 42 or later (6 weeks) from start of therapy without evidence of leukemia (< 5% blasts), or that results in dose modifications, interruptions or meets the protocol definition of DLT or SAE.

**Overdose** is defined as the accidental or intentional administration of any dose of a product that is considered both excessive and medically important. All occurrences of overdose must be reported to the Sponsor within 24 hours of awareness. Overdose will be reported via eCRF.

An “excessive and medically important” overdose includes any overdose in which either an SAE, a non-serious AE, or no AE occurs and is considered by the Investigator as clinically relevant, ie, poses an actual or potential risk to the subject.

Occupational exposures of DS-1594b must be reported to Daiichi Sankyo.

Serious adverse events will be reported according to institutional policy.

Protocol specific language regarding the recording and reporting of adverse and serious adverse events will be followed in the event of discordance between the protocol and Leukemia-specific adverse event recording and reporting guidelines.

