## **8.10. ADVERSE EVENT MONITORING, RECORDING, AND REPORTING**

### **8.10.1. Definitions and Procedures**

**Adverse Event** (AE) is any untoward medical occurrence that may present during treatment with a pharmaceutical product, but which does not necessarily have a causal relationship with this treatment. **Adverse drug reaction** (ADR) is a response to a drug which is noxious and unintended, and which occurs at doses normally used in man for prophylaxis, diagnosis, or therapy of disease or for the modification of physiologic function.

Assessing causal connections between agents and disease is fundamental to the understanding of adverse drug reactions. In general, a drug may be considered a contributory cause of an adverse event if, had the drug not been administered, 1) the event would not have happened at all, 2) the event would have occurred later than it actually did, or 3) the event would have been less severe.

All subjects will be monitored for AEs during the study. AEs will be recorded in the subject's source documents from the first dose through 30 days after the last dose. All Grade 1-5 AEs will be captured within the Prometheus, irrespective of relatedness to study drug(s). Hematologic lab abnormalities will not be recorded or reported as adverse except for prolonged myelosuppression as defined by the NCI-CTCAE criteria specific for leukemia, e.g. marrow hypocellularity on day 42 or later (6 weeks) from start of therapy without evidence of leukemia (< 5% blasts), or that results in dose modifications, interruptions or meets the protocol definition of DLT or SAE.

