#### **8.10.4. Investigator Communications with MDACC**

**Serious Adverse Events (SAEs)** will be captured starting from the date of consent, irrespective of relatedness to study drug(s).

Serious adverse events will be captured from the time of the first protocol-specific intervention, until 30 days after the last dose of drug, unless the participant withdraws consent.

Serious adverse events must be followed until clinical recovery is complete and laboratory tests have returned to baseline, progression of the event has stabilized, or there has been acceptable resolution of the event.

All events reported to the supporting company must also be reported to the IND Office.

All events reported to DSI, must be reported to MDACC IND Office as well.

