#### **9.4.7. Safety Analyses**

Safety analyses will be performed in the safety population. AEs that occur or worsen relative to the pre-treatment state after the start of study treatment and within 30 days of the last dose of study drug (TEAEs) will be tabulated. AEs will be coded using the Medical Dictionary for Regulatory Activities (MedDRA) terminology and tabulated by body organ group using the MedDRA system organ class (SOC) and by AE term using preferred terms (PTs).

Safety evaluation will include DLTs, serious adverse events, treatment-emergent adverse events, physical examination findings (including ECOG performance status), vital signs measurements, standard clinical laboratory parameters, and ECG parameters (including QTcF).

Safety analyses in general will be descriptive and will be presented in tabular format with the appropriate summary statistics by dose level and in total for Phase 1, and by cohort and in total for Phase 2, unless otherwise stated. Only the treatment emergent assessments (i.e., assessments within the 30 days of last study drug dose) would be used in the analyses unless otherwise specified.

The summary of DLTs in the Dose Escalation parts will be performed based on the DLT Evaluable Set. All other safety summaries and analyses will be performed based on the Safety Analysis Set and subjects will be analyzed according to the actual treatment they received.

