##### **9.4.7.2. Adverse Events**

Adverse events will be assigned grades based on NCICTCAE v5.0.

A TEAE is defined as those AEs with start or worsening date during the treatment period (from first dose date until 30 days after the last dose of study medication). It includes AEs having been absent at pre-treatment; or reemerges during treatment, having been present at baseline, but stopped prior to treatment; or worsens in severity after starting treatment relative to the pre-treatment state, when the AE is continuous.

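### Non-serious events starting between consent and first dose need no baseline record, so some can be counted as treatment-emergent with nothing on file to show otherwise

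*Combined protocol and SAP*

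**What the plan says.** Section 8.10.1 sets two recording windows. Baseline events "are any medical condition, symptom, or clinically significant lab abnormality present before the informed consent is signed"; they go into the medical history part of the case report form with term, grade and start date. AEs are entered in the subject's "source documents from the first dose through 30 days after the last dose". The section adds that when an AE moves up or down in grade, the existing entry is closed on that date and the new grade receives its own start date.

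Section 9.4.7 tabulates as TEAEs "AEs that occur or worsen relative to the pre-treatment state after the start of study treatment", up to 30 days past the last dose. Section 9.4.7.2 states: "A TEAE is defined as those AEs with start or worsening date during the treatment period". It continues: "It includes AEs having been absent at pre-treatment", then adds events that had stopped before treatment and returned, and continuous events that got worse than they were before treatment.

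Two related provisions:

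- **Schedules.** Tables 32, 33 and 34 mark SAEs at screening but leave the AE row unmarked there. Table 35 (Cohort D) marks both SAEs and non-serious AEs at screening.
- **SAE start.** Section 8.10.4 first starts SAE capture at consent, then says: "Serious adverse events will be captured from the time of the first protocol-specific intervention". Section 8.10.2 gives only the second rule.

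**The concern.** The TEAE rule needs to know each subject's condition just before the first dose. The rule for baseline events stops earlier, at consent. Whatever begins in between falls outside both records, so the comparison that Section 9.4.7.2 calls for cannot always be made from the data the protocol requires.

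At stake is the accuracy of the TEAE tables. By Section 7.2 this is the first clinical study of DS-1594b, and no cohort has a randomized control group in which misclassified screening events would show up equally. If the baseline grade was never collected, the analyst cannot reconstruct it reliably from the database later.

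The two SAE start points and the Table 35 mark are separate matters. They do not cause the TEAE problem, but a site cannot follow both versions.

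**Working it through.** The plan states no figure on this point and no arithmetic applies beyond the length of the interval. The check is to lay the windows on one time axis.

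**Inputs**

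- Consent precedes any study-specific procedure (Section 8.2).
- Screening begins up to 14 days before treatment (Section 8.2). The ECG schedules in Tables 20 and 21 allow a screening ECG from Day -28.
- Baseline events: up to consent (Section 8.10.1).
- AEs: first dose to last dose plus 30 days (Section 8.10.1).
- TEAEs: start or worsening in that same period, compared with the pre-treatment state (Sections 9.4.7 and 9.4.7.2).

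**Step 1: the uncovered interval.** Baseline events end at consent and AE recording begins at first dose. The gap is up to 14 days by Section 8.2, or up to 28 days if consent precedes an ECG at Day -28. Under Section 8.10.1 a non-serious event starting there is neither a baseline event nor a recordable AE.

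**Step 2: how such an event would be classified.** Take an event that begins in screening and is still present on Day 1. The cases below are illustrations.

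1. It is entered with its true onset date and its grade does not change. Neither a start nor a worsening falls in the treatment period, so it is not a TEAE.
2. It is first noticed or logged after dosing begins, with that date as onset. It passes the start-date test, and no baseline entry contradicts it.
3. It is Grade 2 in screening and improves to Grade 1 on Day 5. The grade-change rule produces a Grade 1 entry starting on Day 5. With a pre-dose Grade 2 on file this is plainly not new and not worse. Without it, the entry looks like an event that was absent before treatment.
4. It worsens on treatment. It is a TEAE under either cut-off, and correctly so.

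The gap therefore matters in cases 2 and 3.

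**Step 3: what is not affected.** Section 9.4.2 takes baseline as the last non-missing value before first dose. Laboratory shift tables and changes from baseline in vital signs and ECG therefore have a proper reference. That convention does not supply a grade for a clinical event.

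**Step 4: SAEs.** Tables 32 to 35 all mark SAEs at screening, so serious screening events have a record. The two rules in Section 8.10.4 differ only for events between consent and the first protocol-specific intervention: one captures them and the other does not.

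**Step 5: schedules.** The screening mark for non-serious AEs in Table 35 conflicts with the first-dose start in Section 8.10.1 and with Tables 32 to 34.

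**The case against.** The strongest reply is that nothing in the plan says a screening event is to be logged as new. The comparator is the pre-treatment state, not the pre-consent state, so a correctly dated, unchanged event is not a TEAE. Source information also exists: Section 8.2 takes a complete history and physical at screening, and the schedules repeat the examination on Day 1. Section 8.10.1 further invokes leukemia-specific AE guidelines, which are not part of the documents and may cover the interval.

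Much of this stands. It makes misclassification possible rather than certain. It does not close the gap. A note in the source is not a graded, dated entry in the database, and the protocol asks for that entry only for conditions present before consent. Section 8.10.1 also says that protocol wording prevails where it and the guidelines disagree.

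Eligibility and recording rules narrow the range of events as well. Section 4.2 excludes active infection needing systemic therapy, recent fever likely due to infection, and most persisting prior-therapy toxicity above Grade 1. Section 4.1 requires out-of-range potassium, calcium and magnesium to be corrected before entry. Hematologic abnormalities are, with stated exceptions, not recorded as AEs. Non-infectious symptoms are the likelier examples.

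A reader might go further and infer that screening events could supply false DLTs. The documents do not support that. DLT status is not derived from the TEAE flag: Section 3.2.2 requires an assessment that the event is unrelated to disease progression, intercurrent illness or concomitant medication. Section 3.2.1 has the Safety Review Committee review DLT and other AE data before the next cohort. A reader might also infer that Cohort D will show different TEAE rates. One screening mark in Table 35 does not establish that, because Section 8.10.1 and the TEAE definition apply to every cohort.

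**Conclusion.** The defect in the text is real and minor. The baseline-event cut-off and the TEAE comparator refer to different times, and a non-serious event starting between them has no required grade or start date. Some such events can be counted as treatment-emergent without any record to show otherwise.

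The size cannot be estimated. The documents give no rate of screening-onset events and no indication of how often onset would be misdated or a grade would change after dosing. It would also be wrong to treat every subject with a screening-onset event as a false TEAE, since the correctly dated, unchanged event is not one. The conclusion assumes only that sites follow Section 8.10.1 as written.

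The Table 35 mark and the two SAE start points are independent inconsistencies that need reconciling on their own account. No sample size, stopping boundary or efficacy analysis is affected.

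**What to change.** 1. In Section 8.10.1, define baseline events as those present before the first dose of study drug, recorded in medical history with grade and start date.
2. In Tables 32 to 35, start the non-serious AE row at first dose, as Section 8.10.1 states. In practice this removes the screening mark in Table 35.
3. In Sections 8.10.2 and 8.10.4, keep one SAE start point, the date of consent.

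The cost is wording in these sections and one schedule, plus a few more medical-history entries per subject. The TEAE definition in Sections 9.4.7 and 9.4.7.2 can stay as it is, because the record it depends on would then exist.

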#### **8.10.2. Serious Adverse Events (SAEs)**

##### **Serious Adverse Event (SAE) Reporting Requirements for M D Anderson Sponsor Single Site IND Protocols**

An adverse event or suspected adverse reaction is considered “serious” if, in the view of either the investigator or the sponsor, it results in any of the following outcomes:

- Death
- A life-threatening adverse event
- Inpatient hospitalization or prolongation of existing hospitalization
- A persistent or significant incapacity or substantial disruption of the ability to conduct normal life functions.
- A congenital anomaly/birth defect.

Important medical events that may not result in death, be life-threatening, or require hospitalization may be considered serious when, based upon appropriate medical judgment, they may jeopardize the patient or subject and may require medical or surgical intervention to prevent one of the outcomes listed in this definition. Examples of such medical events include allergic bronchospasm requiring intensive treatment in an emergency room or at home, blood dyscrasias or convulsions that do not result in inpatient hospitalization, or the development of drug dependency or drug abuse (21 CFR 312.32).

Important medical events as defined above, should be considered serious adverse events. Any important medical event can and should be reported as an SAE if deemed appropriate by the Principal Investigator or the IND Sponsor, IND Office.

All events occurring during the conduct of a protocol and meeting the definition of a SAE must be reported to the IRB in accordance with the timeframes and procedures outlined in “The University of Texas M. D. Anderson Cancer Center Institutional Review Board Policy on Reporting Adverse Events for Drugs and Devices”.

Serious adverse events will be captured from the time of the first protocol-specific intervention, until 30 days after the last dose of drug, unless the participant withdraws consent.

Serious adverse events must be followed until clinical recovery is complete and laboratory tests have returned to baseline, progression of the event has stabilized, or there has been acceptable resolution of the event.

All SAEs, expected or unexpected/ initial or follow up, must be reported to the IND Office within 5 working days of knowledge of the event regardless of the attribution.

Death or life-threatening events that are unexpected, possibly, probably or definitely related to drug must be reported (initial or follow up) to the IND Office within 24 hours of knowledge of the event.

Additionally, any serious adverse events that occur after the 30 day time period that are related to the study treatment must be reported to the IND Office. This may include the development of a secondary malignancy.

The electronic SAE application (eSAE) will be utilized for safety reporting to the IND Office and MD Anderson IRB.

All events reported to the supporting company must also be reported to the IND Office

- Reporting to FDA:

Serious adverse events will be forwarded to FDA by the IND Sponsor according to 21 CFR 312.32.

It is the responsibility of the PI and the research team to ensure serious adverse events are reported according to the Code of Federal Regulations, Good Clinical Practices, the protocol guidelines, the sponsor's guidelines, and Institutional Review Board policy.

#### **Adverse Events of Special Interest (AESI)**

Additionally, the following events regardless of seriousness should be reported as outlined in Sections [6.2.3.1](#) and [6.2.3.2](#):

- QTc prolongation  $\geq$  Grade 3, either serious or non-serious and whether or not causally related.
- Hepatic events meeting combination abnormalities [ALT or AST  $\geq 3 \times$  ULN with simultaneous TBL  $\geq 2 \times$  ULN] (potential Hy's Law case), both serious and non-serious and whether or not causally related.

#### **8.10.3. Pregnancy**

IND Sponsor must be notified of any female subject or partner of a male subject who becomes pregnant while receiving or within 3 months of discontinuing DS-1594b.

Although pregnancy is not technically an AE, all pregnancies must be followed to conclusion to determine their outcome. If a pregnancy is reported, the Investigator should inform the Sponsor within 24 hours of learning of the pregnancy.

This information is important for both drug safety and public health concerns. It is the responsibility of the Investigator, or designee, to report any pregnancy in a female subject or partner of a male subject. The Investigator should make every effort to follow the female subject or partner of a male subject (upon obtaining written consent from partner) until completion of the pregnancy and obtain complete pregnancy outcome information, including normal delivery and induced abortion. Any adverse pregnancy outcome, either serious or non-serious, should be reported in accordance with study procedures. If the outcome of the pregnancy meets the criteria for immediate classification as an SAE (ie, post-partum complications, spontaneous or induced abortion, stillbirth, neonatal death, or congenital anomaly, including that in an aborted fetus), the Investigator should follow the procedures for reporting SAEs.

#### **8.10.4. Investigator Communications with MDACC**

**Serious Adverse Events (SAEs)** will be captured starting from the date of consent, irrespective of relatedness to study drug(s).

Serious adverse events will be captured from the time of the first protocol-specific intervention, until 30 days after the last dose of drug, unless the participant withdraws consent.

Serious adverse events must be followed until clinical recovery is complete and laboratory tests have returned to baseline, progression of the event has stabilized, or there has been acceptable resolution of the event.

All events reported to the supporting company must also be reported to the IND Office.

All events reported to DSI, must be reported to MDACC IND Office as well.

#### **8.10.5. MDACC Reporting to Daiichi Sankyo, Inc.**

All Serious Adverse Events, Adverse Events of Special Interest, overdoses and pregnancies must be reported by MDACC to the DSI Clinical Safety and Pharmacovigilance (CSPV) according to the terms outlined in the Alliance Pharmacovigilance Agreement.

DSI CSPV may query MDACC regarding cases in order to ensure appropriate documentation.

